# 10. Study management

## 10.1 The Norwegian Directorate of Health

The Norwegian Directorate of Health is responsible for the practical implementation of the trial, and will:

- Define the scope of the trial
- Recruit participating municipalities
- Assist the participating municipalities in designing and setting up the service
- Follow the implementation of the project (incl. recruitment targets)
- Partially finance the local projects
- Establish a reference group for the trial

## 10.2 The researchers

The University of Oslo, Oslo Economics and the Norwegian Centre for Rural Medicine (NCRM) have joint responsibility for developing and implementing the study design. The University of Oslo and Oslo Economics have joint responsibility for data processing. The University of Oslo, Oslo Economics and the Norwegian Centre for Rural Medicine (NCRM) will:

- Develop the research design
- Apply for necessary approval from ethical committees and data protection services
- Draw up data processor agreements with participating municipalities and third parties involved in the study
- Conduct the evaluation as described in this study protocol
- Present results in three reports

## 10.3 The participating municipalities

- Develop the service
- Implement and run the service according to protocol
- Recruit participants
- Conduct study initiation meetings
- Facilitate data collection

## 10.4 Study amendments

If it is necessary for the study protocol to be amended, the amendment and/or the new version of the study protocol must be notified to and approved by the management at the University of Oslo and Oslo Economics and the Norwegian Centre for Research data (NSD) according to EU and national regulations.

## 10.5 Audit and inspections

Authorized representatives of the Data Protection Authority may visit the centers to perform inspections. Likewise, representatives from the Norwegian Directorate of Health may visit the municipalities to perform audits. The purpose of an inspection is to systematically and independently examine study-related activities and documents to determine whether these activities were conducted, and data were recorded, analyzed and accurately reported according to the protocol, and any applicable regulatory requirements.

## 11. Risk assessment

There are several risks connected with the telehealth trial. Risks are closely monitored by the NDH and the researchers. The following are among the most central risks identified:

### **Recruitment of participants**

There is a worry that the recruitment target will not be reached within June 30, 2020. However, the NDH and the local centers have detailed plans for recruitment and follow the development closely. At the same time, the centers have signalized that they aim at recruiting more patients than they originally signaled.

In December 2019, the NDH will evaluate the recruitment process. If recruitment is insufficient, one option is to terminate the trial.

### **Spillover of treatment to control group**

A drawback of the randomization strategy is that there is a risk that the intervention spills over to the control group. The knowledge of the intervention might affect both the type and extent of the care that the control group receives. The health and care personnel are made aware of this issue. The patients in the study have a need for health care services, and the protocol is that they receive "standard clinical care". In practice, what this means, depends on the patient's medical condition and needs.

It is important for the interpretation of the results of the study, that the actual treatment that the control group receives is studied. This is done in many ways. First, we collect information on the use of health and care services for the intervention and control group from national health registers. Second, we will interview health and care personnel about the follow-up of patients in the control group. Third, we will conduct interviews with patients in the control group about their experiences. Fourth, we plan to compare the outcomes of the treatment and the control group in the study to a register-based control group containing patients with similar characteristics in non-participating municipalities. Thus, we will have an additional control group that is not affected by the trial. This comparison is performed using data from the related evaluation of primary health teams.

If the patients in the control group receive more comprehensive follow-up than they would in the absence of the reform, the effects of the intervention are likely *underestimated*, rather than overestimated.

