**Table 1: Study objectives and related endpoints**

	Objectives	Outcomes	Assessments
Primary	To assess whether patients who are followed up using telehealth experience an improved health state (or lower reduction in health state for patients with deteriorating health)	Primary 

• Health related quality of life (EQ-5D)

 Secondary 

• Physical functioning

• Sleep

	Section 6.1

---

	compared to patients receiving standard clinical care.	• Coping	
Primary	To assess whether patients who are followed up using telehealth are more satisfied with the health care services than patients receiving standard clinical care.	Primary • Overall satisfaction with treatment and follow-up Secondary • Satisfaction with the telehealth technology (only in the intervention group) • Satisfaction with health care personnel • Patient involvement • Perceived benefits	Section 6.2
Primary	To assess whether patients who are followed up using telehealth utilize less healthcare resources than patients receiving standard clinical care	Primary • Health and care cost per person Secondary • Use of health and care services	Section 6.3
Explanatory	To evaluate the organization of the service	• Describe and evaluate the service: organization, cooperation between health and care providers, user involvement, technological solutions	Section 6.4
Explanatory	To evaluate the cost-effectiveness of telehealth compared to standard clinical care	• Summarize costs and benefits of the intervention and comparator strategy • Evaluate cost-effectiveness • Compare cost-effectiveness across local projects	Section 6.5

---

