### **Total health and care cost per person**

Total costs for health and care services per person are calculated on a yearly basis using publicly available statistics of cost related to the use of health and care services and actual use of health and care services. Total costs are also split between different parts of the health service (primary and specialist health care services).

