From the previous trial, we know that after 5 to 9 months of telehealth follow-up, users reported self-rated health state at 0.612 (on a scale of 0 to 1), and this decreased by an average of 0.105 units from start-up. Thus, the users of medical distance monitoring experienced a decrease in self-assessed health status, but our hypothesis is that a control group would experience an even greater decline. In panel A, we show the required sample size to identify a statistically significant effect at a 5 % level with strength of 80 % for three different outcomes: that the action group reports 0.05, 0.08 or 0.105 lower reduction in self-assessed health status during the follow-up period compared to with the control group. In panel B, the desired sample size is calculated based on the number of GP consultations per year. In the previous trial, the participants experienced an average reduction of 2 visits per year compared to an average of 14.66 regular visits per year. We assume that the control group will be able to experience unchanged or increased number of GP consultations, and therefore calculate strength based on scenarios with a difference of 2-4 doctor visits. In panels C and D, the same calculations are repeated for the number of outpatient consultations and emergency days. The same reasoning applies.

Our assessment is that a sample size of 600 is enough to estimate significant effects of telehealth, but that a larger sample is preferable. The NDH and the participating municipalities are informed about this and work to increase the number of participants.

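### Section 11's statement that extra follow-up of controls makes the effects likely underestimated is not supported for the primary cost endpoint or for service use, where the net direction of bias is unknown

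*Combined protocol and SAP*

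**What the plan says.** Under its spillover heading, section 11 accepts that the trial may change how controls are treated: "The knowledge of the intervention might affect both the type and extent of the care that the control group receives". It then says how results should be read in that case. The condition is "If the patients in the control group receive more comprehensive follow-up than they would in the absence of the reform"; the conclusion is that "the effects of the intervention are likely *underestimated*, rather than overestimated". No endpoint is named and none is excepted.

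Table 1 lists three primary objectives. The third asks whether telehealth patients "utilize less healthcare resources than patients receiving standard clinical care", and its primary outcome is "Health and care cost per person". Section 6.3 explains how that outcome is built: "Total costs for health and care services per person are calculated on a yearly basis", from "publicly available statistics of cost related to the use of health and care services and actual use of health and care services". The use outcomes listed there include GP consultations, home-service visits, outpatient consultations and hospital admissions.

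Section 9.2 gives each GP a separate stack of three intervention and three control envelopes, with open allocation, so the same GP can be treating patients in both arms.

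**The concern.** The three primary endpoints do not share a direction of benefit. For EQ-5D and satisfaction, extra attention to controls plausibly improves their scores and narrows the gap, so the effect is understated. For use and cost, the extra attention is part of what is measured. A GP visit or outpatient check that a control patient receives because of the trial adds to control-arm use and makes telehealth look cheaper by comparison.

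The results are meant to inform national implementation (sections 1.2 and 2), and the cost-benefit analysis draws on the effect-study data (section 6.5). Read through section 11 as written, a cost saving would seem to have survived a bias working against it, when part or all of it could be additional care given to controls because of the trial.

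**Working it through.** **Direction by endpoint.** Let D0 be the intervention-minus-control difference without spillover, s the change that spillover causes in the control mean, and D the observed difference. Then D = D0 − s.

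- EQ-5D and satisfaction: benefit is D > 0. Extra follow-up plausibly gives s ≥ 0, so D ≤ D0 and the benefit is understated. Section 11 is reasonable here.
- Contacts that make up the follow-up (GP, home-service, outpatient): benefit is D < 0. Extra follow-up gives s > 0, so D is more negative and the saving is overstated.
- Admissions or inpatient days averted by the follow-up: s < 0, so the saving is understated.
- Total cost: s is the sum, over services, of unit cost times the change in control use. The terms have opposite signs, and the documents give neither unit costs nor spillover sizes. The sign is undetermined.

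**Reproducing the plan's figures.** The disputed sentence has no figure of its own, so Table 7 supplies the scale. With two-sided 5% and 80% power, n per arm = 2 × [(1.960 + 0.842) × SD / difference]².

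- Panel B, GP consultations, SD 15.21, differences of 2, 3 and 4: 908, 404 and 227, matching the table exactly.
- Panel C, outpatient consultations, SD 4.15, difference 0.5: 1082 after rounding up, against 1081 stated.
- Panel D, emergency inpatient days, SD 12.43, difference 2: 607 after rounding up, against 606 stated.

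**Scale of spillover needed.** The means come from telehealth users in the earlier trial (section 9.1) and serve only as a yardstick.

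- GP consultations: 2 / 14.66 = 13.6%. A rise of that size in controls equals the smallest panel B difference, with no telehealth effect at all.
- Outpatient consultations: 0.5 / 2.34 = 21%. The same holds for the smallest panel C difference.

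**Chance of a significant apparent saving in GP visits.** Take 300 per arm (600 allocated 1:1) and complete data. SE = 15.21 × √(2/300) = 1.242, and P = Φ(−1.96 − D/SE). The spillover of 0 to 4 visits a year is an assumed range.

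| Extra control visits | D if true effect is 0 | P | D if true saving is 2 | P |
|---|---|---|---|---|
| 0 | 0 | 2.5% | −2 | 36% |
| 1 | −1 | 12% | −3 | 68% |
| 2 | −2 | 36% | −4 | 90% |
| 3 | −3 | 68% | −5 | 98% |
| 4 | −4 | 90% | −6 | 99.8% |

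The sign can also reverse: a true increase of 1 visit with 2 extra control visits shows as a saving of 1 (D = 1 − 2 = −1).

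**The opposite case.** For emergency inpatient days, SE = 12.43 × √(2/300) = 1.015. A true saving of 2 days is significant with probability 50%. If the extra follow-up averts 1 day in controls, the observed saving is 1 day and the probability falls to 17%. If it averts 2 days, the observed saving is 0 and the probability is 2.5%. For this outcome section 11's direction is right.

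**The case against.** The sentence is one hedged remark in a risk section. No population, model, test or decision criterion in sections 9.3 to 9.5 refers to it, and nothing says that a saving will be reported as conservative. The same part of section 11 plans to study what controls actually receive: register data for both arms, staff interviews, control-patient interviews, and comparison with a register-based group in non-participating municipalities. Section 6.3 adds at least two pre-recruitment years of use data. Finally, if spillover means that controls get telehealth-like care, and such care lowers use, the cost contrast shrinks too.

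Much of this stands as a limit on how serious the point is. The planned data could reveal a rise in control use. They do not correct the stated direction, however, and section 11 does not link them to the cost endpoint. The contamination reading does not rescue the sentence. Controls are assigned to standard care (section 4.2) and may be reassessed for telehealth only after follow-up (section 5.4). The stated condition is more follow-up, not telehealth.

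The objection also rightly limits the arithmetic. The figures concern secondary use counts, with an assumed spillover, and do not measure bias in total cost.

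A reader might cite section 9.1, "We assume that the control group will be able to experience unchanged or increased number of GP consultations", as the plan's own admission of spillover. It is not one. It is an effect-size assumption about how controls would fare beside telehealth users and says nothing about trial-induced care.

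**Conclusion.** The direction stated in section 11 is reasonable for health state and satisfaction and unsupported for the primary cost endpoint and the service-use outcomes. For those, extra control contacts push towards an apparent saving, averted admissions push against it, and the documents do not settle the balance. As a scale only, and with spillover size assumed, about 2 extra GP visits (13.6%) or 0.5 extra outpatient visits (21%) a year in controls matches the smallest difference the plan considered for that outcome. The chances of significance further assume 300 per arm, complete data and a normal approximation.

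Two stronger readings are tempting. One is that section 11 claims extra follow-up can only shrink effects; the text says this is likely, not certain. The other is that spillover must inflate the cost saving; section 6.3 counts admissions as well as contacts, so the net effect could go either way. What remains is that an unknown direction does not justify the label of likely underestimation.

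**What to change.** In section 11, limit the underestimation sentence to health state and satisfaction. Add that for service use and cost the bias from extra control follow-up can go either way. State that a cost saving will not be described as conservative on the ground of spillover.

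As descriptive support, report by service type, with confidence intervals, the control arm's change from its pre-recruitment years beside the change in the register-based group. Do this only where that group's data cover the service and period. Section 11 takes the group from a related evaluation without stating its coverage, and Table 3 lists municipal record-system data only for participating municipalities. Interpret the table with the caution that section 9.3 already asks for in non-randomised comparisons. It should not trigger an automatic bar on attributing the randomised difference to telehealth: section 6.3 lists eleven use outcomes, some of which would differ by chance, and a non-randomised comparison should not override the randomised one.

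The cost is a few sentences and one descriptive table, with no new patients and no design change. The downside is that a cost saving may have to be reported with less certainty.

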### **Heterogeneity in the trial**

This telehealth trial is less rigorously designed than many conventional randomized control trials. There is variation in the delivery of the intervention (telehealth), in the follow-up of the control group, and in the study population. This poses some challenges in the analysis of the data, and effects must be interpreted as averages over different types of interventions and groups of patients.

### **Data management**

The data management of the study is challenging. Data are collected and linked from several sources, at several points in time. This requires good procedures for data collection and management. A data management plan has been developed.

## 12. Ethical and regulatory requirements

### 12.1 Privacy Policy

It is the joint responsibility of the University of Oslo and Oslo Economics to conduct a Data Protection Impact Assessment (DPIA). A DPIA was conducted together with the Norwegian Centre for Research data (NSD) in

January 2019. The DPIA concludes that the data collection and storage within the project is conducted in accordance with the GDPR.

## 12.2 Informed consent procedure

The research group and/or the project administration is responsible for giving the patients full and adequate verbal and written information about the nature, purpose, risk and benefits of the trial. They are informed about the strict confidentiality of their patient data, but that their medical records may be reviewed by the researchers for evaluation purposes.

It is emphasized that the participation is voluntary and that the patient can refuse further participation in the trial whenever she/he wants. This will not prejudice the patient's subsequent care. Participants who withdraw their consent may request that all information collected be deleted, unless they are included in publications or articles.

Patients who have not signed the written consent form cannot obtain equipment from the municipality, and consent is thus a prerequisite for participation in the trial. The consent form is enclosed in Appendix A.

A copy of the signed consent statement is given to the patient. Signed consent statements are collected in a suitable folder by the project administration and will also be scanned and stored electronically at the project administration.

Written consent will be also obtained from participants in the evaluation other than those in the intervention and control group. This includes interviewees, such as GPs, employees and the follow-up service, other representatives from the health and care service and relatives.

## 12.3 Patient Identification

The project administration keeps a record of everyone who has signed consent. This overview includes name, date of birth, and birth number and address. The personal information is stored in a separate password-protected document.

Each participant gets a unique serial number that acts as a link between different data sources. The researchers will not have access to directly identifiable information about the patients.

## 12.4 Confidentiality

Healthcare professionals participating in the trial have a duty of confidentiality towards the patients. In interviews with health personnel, there will be no questions about individual patients.

## 12.5 Ethical committee approval

The Regional committees for medical and health research ethics (REK) has assessed the study protocol. In the decision from 26.11.2018, REK stated that the trial falls outside REK's area of responsibility as it was deemed as health services research and not medical research.

## 12.6 Other regulatory approvals

The protocol will be registered in [www.clinicaltrials.gov](http://www.clinicaltrials.gov) in summer 2019.

# 13. Trial sponsorship and financing

The trial is financed by the Norwegian Directorate of Health and the participating municipalities. The evaluation of the trial is fully financed by the Norwegian Directorate of Health.

## 14. Publication Policy

The results of the trial will be published in two midterm reports and a final report which will be submitted to the Norwegian Directorate of Health (see chapter 15).

We will also consider submitting the results for publication in international peer-reviewed journals.

## 15. Overall progress plan

[figure not shown]
The participating municipalities were recruited in the spring of 2018. The summer and autumn of 2018 were devoted to service development and evaluation design. Recruitment of users and evaluation of the measure started in February 2019. The follow up period ends in the summer of 2021. The exact end date depends on the contract between the Directorate of Health and the individual municipalities.

Table 8 shows important milestones in the evaluation, and Table 9 contains an overview of the progress of the evaluation.

**Table 8: Important milestones**

Milestone	Date
Recruitment starts	01.02.2019
First midterm report	01.03.2020
Second midterm report	01.03.2021
Recruitment ends	30.06.2020
Final report	01.11.2021
Last survey is posted	30.06.2021
Final report to the NDH	01.12.2021
Register data collection terminated	31.12.2022
Project ends	31.12.2022
Data is deleted	31.12.2024

**Table 9: Overall progress plan**

Project administration

Project meetings

Meetings with sponsor and stake holders

Project administration n.e.c.

## Appendix B: Participant questionnaire

ANONYMOUS IDENTIFIER \* x x x x \*

### Telehealth trial: Questionnaire for participants

You receive this questionnaire because you have agreed to participate in a trial of telehealth.

As part of the trial, you will receive a questionnaire about every six months. You will receive a total of four questionnaires during the follow-up period. If you do not return the questionnaire within one week, you will first receive a reminder by mail, and then a reminder by phone. Norsk Gallup manage the survey on behalf of the researchers.

The questionnaire is about your physical and mental health, your experience and satisfaction with the follow-up of your health, as well as background information about you.

**Your answers are of great importance, and we appreciate your participation!**

If you have any questions related to the survey, please contact [name], project member at Oslo Economics, by email at [[contact]](mailto:[contact]).

#### Physical and mental health

**1. How often do you engage in physical activity of such intensity that you become somewhat breathless and/or sweaty?**

- Every day
- 4-6 times per week
- 2-3 times per week
- Once a week
- 1-3 times per month
- Less than once a month
- Never

**2. To what extent do you engage in physical everyday activities such as gardening, gardening, walking or cycling as a transport?**

- a. To a small extent
- b. To some extent
- c. To a large extent
- d. Do not know

